- 4) Assess the interventional cohort's preoperative demographics and collected covariates for association with the ease or difficulty of mitigating observed cerebral desaturation events.

Exploratory analyses will include performing all possible comparisons of the two groups based upon all collected perioperative variables to examine the potentially significant relationships between the collected clinical variables representing surrogates of organ perfusion/function and cerebral oximetry desaturations (AUCrSO2). The following exploratory endpoints will be assessed:

- Logistic regression analysis to determine the most relevant AUCrSO2 desaturation value(s) associated with any detrimental clinical outcome(s) monitored in this study
- Logistic regression analysis to determine the most relevant AUC blood pressure values associated with any detrimental clinical outcome(s) monitored in this study
- Comparison of baseline rSO2 values (room air and oxygen supplemented) to all collected clinical variables to assess for possibly significant associations
- Explore the potential impact of rSO2 monitoring on changing the surgical conduct of the procedure

**Methodology:** Single center, prospective, randomized, controlled clinical pilot study

**Number of Subjects:** 100 subjects with balanced randomization (1:1) to control (blinded NIRS data) or intervention (open NIRS data) cohorts

**Main Criteria for Inclusion:** Elderly patients (> 65 years of age) scheduled for a thoracic surgical procedure at UHCMC that will involve SLV.

**Duration of Treatment:** Cerebral oximetry monitoring will begin with an assessment of both room air and oxygen supplemented bi-frontal baseline NIRS values and continue through the surgery to either PACU discharge or the initial 12 hours of post surgical ICU treatment. Mini Mental Status exam testing and Delirium testing with the Confusion Assessment Method will occur preoperatively and postoperatively through post-operative day (POD) #3 (or discharge if that occurs sooner than POD #3).

Enrolled subjects will be followed during the index hospitalization and will undergo a 30 day follow up telephone interview to assess their progress following hospital discharge.

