### **7 STUDY DESIGN**

#### **7.1 Study Design**

This study is a single center (University Hospitals Case Medical Center), prospective, randomized, controlled pilot study of elderly thoracic surgical patients undergoing procedures involving the use of SLV. A total of 100 eligible subjects will be randomized in a balanced fashion (1:1) to either the control cohort that will have electronically blinded bi-frontal cerebral oximetry monitoring or the intervention cohort that will have open bi-frontal cerebral oximetry monitoring with a predefined intervention protocol for observed desaturations of greater than 20% of established oxygen supplemented baseline values (see Appendix C). Both the control and intervention groups will have baseline NIRS data obtained in an unblinded fashion. The study will be divided into four separate periods that include screening, baseline acquisition, intraoperative and immediate postoperative and the postoperative follow up period.

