  - AUCSpO2 < 80% regardless of intraoperative FiO2 values ○
  - AUCSpO2 < 75% regardless of intraoperative FiO2 values ○
  - AUCSpO2 < 70% regardless of intraoperative FiO2 values ○
- Use of any intraoperative, intravenous vasopressor and/or inotropic agent (as assessed by amount of time in minutes on any IV drug support regardless of dose and assessed by total dose of drug delivered to patient)
- Intraoperative urine output in any patient with an indwelling foley catheter as assessed by mLs urine/kg/hr for total time in operating room
- Need for intraoperative red blood cell transfusion (as assessed by number of RBC units transfused)
- Observed desaturation prompted change in surgical procedure (e.g., the surgery was paused to inflate the collapsed lung to improve systemic tissue oxygenation) ●  
● Occurrence of any intraoperative stroke or transient ischemic attack (as assessed by documented clinical neurological assessment or cerebral imaging study) ● Any

observed intraoperative myocardial ischemia or infarction (as assessed by intraoperative ECG changes and/or myocardial biomarkers (i.e. troponin increase)

- ❶ Area under the curve of any observed intraoperative hyperglycemia ( $AUC_{Glu} > 110 \text{ mg/dL}$ ) in patients with a documented history of either type I or II diabetes mellitus ❶ Any occurrence of intraoperative atrial fibrillation (capturing duration of atrial fibrillation and whether treatment was required)
- ❶ Total time spent in operating room
- ❶ Total amount of narcotic administered in the operating room
- ❶ Total volume of crystalloid administered in the operating room
- ❶ Total volume of colloid administered in the operating room
- ❶ Anti-emetic medications administered in the operating room
- ❶ Surgical procedure performed
- ❶ Time on single lung ventilation ❶

Intraoperative Use of epidural catheter

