# 9 SUBJECT SELECTION

## 9.1 Study Population

A total of 100 evaluable subjects will be enrolled into this protocol. Patients at least 65 years of age who are scheduled to undergo non-emergent, thoracic surgical procedures planned to involve the use of single lung ventilation will be evaluated in this study.

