### 9.1.1 Inclusion Criteria:

1. Any male or female patient  $\geq 65$  years of age and able to provide informed consent (or consent may be provided by a legally authorized representative) who is scheduled for a thoracic surgical procedure that is expected to involve the use of intraoperative single lung ventilation (SLV)
2. Able to adequately complete a baseline mini-mental status examination (MMSE)

3. Able to complete a baseline confusion assessment method (CAM) examination
4. Able to obtain bi-frontal baseline rSO2 values prior to induction of anesthesia

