## **11.1 Protocol Assessments and Procedures – Screening Period**

### **11.1.1 General Screening Period Description**

Screening of potential subjects will occur prior to the planned surgical procedure to allow individuals time to consider their participation. Subjects will be screened from the daily Mather Operating Room printed schedule. Subjects scheduled to undergo surgical procedures that appear to meet the primary inclusion criteria will be approached for additional screening in the Mather Preoperative Area. An IRB registered investigator or nurse coordinator will approach the patient if they are willing to consider listening to a brief description of the study. Patients who verbally agree to learn more about the study will then have a discussion with the IRB registered study investigator or nurse coordinator which includes the details of the study explained in clear and concise language. During this conversation the voluntary nature of any individual's participation will be clearly communicated. Additionally, the discussion will include a description of what the patient's participation will entail, including the voluntary nature of their participation, their ability to withdraw at any time, the confidential nature of their participation, the procedures that will occur among study participants, the information that will be collected from participants and all of the risks and benefits associated with their participation in the trial. Additionally, the study staff will explain to the patient how their hospital care may be different if they choose to participate in the study, including the fact that they will be randomized to either the control group or the intervention group with a 50% chance of being assigned to either group. The implications of being assigned to either group will be discussed.

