### 11.2.2 Randomization

Next, each subject will be randomized in a balanced fashion (1:1) to either the control group or the intervention group. Randomization will occur through the use of a blinded envelope technique at which time each subject will acquire a unique study identifier for their study records.

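### The scheduled procedure is neither recorded before randomisation nor used in the arm comparison, so precision is lost and chance imbalance in surgical mix goes unaccounted for

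*Combined protocol and SAP*

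**What the plan says.** **Eligibility.** Section 9.1.1 admits patients "scheduled for a thoracic surgical procedure that is expected to involve the use of intraoperative single lung ventilation (SLV"). Section 9.1 adds one limit, that subjects are "scheduled to undergo non-emergent, thoracic surgical procedures planned to involve the use of single lung ventilation". The exclusions in 9.1.2 do not narrow the type, extent or approach of the operation.

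**Allocation.** Under 11.2.2, "each subject will be randomized in a balanced fashion (1:1) to either the control group or the intervention group", and "Randomization will occur through the use of a blinded envelope technique". Neither this section nor 7.1 or 7.2.2 describes strata, blocks or minimisation.

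**What is recorded.** The preoperative list in 11.1.3.1 covers demographics, comorbidities, creatinine, haemoglobin and LVEF, but not the planned operation. "Surgical procedure performed" appears in 7.4.1.1, and the procedure appears again in 11.3.3.1; both are intraoperative lists. Time on single lung ventilation is also intraoperative.

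**Effect of monitoring on the surgery.** Section 7.4.1.1 also records changes in the procedure prompted by desaturation. The synopsis plans to explore the effect of monitoring "on changing the surgical conduct of the procedure".

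**Analysis.** The synopsis and Section 15 compare observed clinical data between arms by the Wilcoxon rank-sum test. The stepwise logistic model relates desaturations to clinical variables; it is not an arm comparison adjusted for case mix.

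**Availability of the planned procedure.** Section 11.1.1 states: "Subjects will be screened from the daily Mather Operating Room printed schedule".

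**The concern.** Many of the listed outcomes plausibly depend on which operation is done: hospital stay, PACU or ICU route, theatre time, narcotic dose, transfusion, return of bowel function, time to wean from oxygen, and the composite through its stay and PACU-time components. With 50 subjects per arm and no stratification, the arms may differ by chance in their share of larger operations, and the planned test takes no account of it.

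This matters because of what the pilot is meant to deliver. Section 6.2 makes its primary objective the identification of outcomes that diverge between arms, so that a larger trial can be built on them. That choice rests on one realised allocation. Because several outcomes may share a dependence on the operation, one imbalance could move several candidates together and look like corroboration, or could mask a real signal.

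The listed procedure variables are poor repair tools. Procedure performed and time on single lung ventilation are both fixed after randomisation, and the plan itself allows that open monitoring may alter the conduct of surgery.

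**Working it through.** **Inputs.** From the documents: 100 subjects allocated 1:1, so 50 per arm (7.1), and rank-sum tests (15). The 0.05 threshold is stated for the regression; I take it as two-sided for the arm comparison. The documents give no power, effect size, SD or procedure mix, so the sample size of 100 cannot be reproduced. Assumed for illustration: one larger-procedure class with prevalence p of 20–50%, shifting a continuous outcome by s = 0.5 or 1.0 within-class SD.

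**1. Chance of imbalance.** With fixed arms of 50 and M subjects in the class, the number x falling in one arm is hypergeometric, and the difference in counts is 2x − M. For even M this difference is always even, so at least 10 points means at least 6 subjects, and at least 15 points means at least 8.

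| Prevalence | ≥10 points | ≥15 points | ≥20 points |
|---|---|---|---|
| 20% | 21.1% | 7.8% | 2.3% |
| 30% | 27.5% | 12.6% | 4.9% |
| 50% | 31.7% | 16.1% | 7.1% |

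**2. Shift compared with noise.** The shift in the arm difference is imbalance × s. The standard error is √(2/50) × √(1 + s²p(1−p)). At s = 1.0 and p = 30% it is 0.2 × √1.21 = 0.22 SD. A 10-point imbalance shifts the contrast by 0.10 SD, and a 20-point imbalance by 0.20 SD, which is 0.20/0.22 = 0.91 of a standard error.

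The same in days, all inputs assumed (40% larger cases staying 3 days longer, within-class SD 3 days):
- A 16-point imbalance has probability 15% for that size or more.
- It shifts mean stay by 0.16 × 3 = 0.48 day.
- Total SD is √(9 + 0.24 × 9) = 3.34 days, so the standard error is 3.34 × √(2/50) = 0.67 day.
- The shift is 0.48/0.67 ≈ 0.7 of a standard error.

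**3. False-positive rate of the unadjusted rank-sum test.** 20,000 simulated unstratified 50/50 allocations per scenario, no treatment effect, p = 30% and 50%:

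| Class effect | Overall | Given ≥10 points | Given ≥20 points |
|---|---|---|---|
| 0.5 SD | 4.9–5.1% | 5.7–6.3% | 6.7–8.0% |
| 1.0 SD | 5.1–5.2% | 8.3–8.6% | 15.0–15.5% |

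**4. Precision lost.** The share of variance explained by class is R² = s²p(1−p)/(1 + s²p(1−p)). By the normal approximation for two means, 50 per arm gives 80% power at (1.96 + 0.84) × √(2/50) = 0.56 total SD. Adjustment divides the standardised difference by √(1 − R²), and power is Φ(0.56/(0.2√(1 − R²)) − 1.96).

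| Class effect | p | R² | Power, unadjusted | Power, adjusted |
|---|---|---|---|---|
| 0.5 SD | 30% | 0.050 | 80% | 81.9% |
| 0.5 SD | 50% | 0.059 | 80% | 82.3% |
| 1.0 SD | 30% | 0.174 | 80% | 86.9% |
| 1.0 SD | 50% | 0.200 | 80% | 87.9% |

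**The case against.** The strongest reply is that randomisation already deals with this. The test's overall error rate is correct, and even a 20-point imbalance with a 1.0 SD class effect moves the contrast by less than one standard error. That stands. A reader might infer from the broad eligibility that case mix can drive the arm contrast; the documents and the arithmetic do not support so strong a statement. What remains is that conditional error rises when an imbalance occurs, and that avoidable variance is left in the comparison.

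A reader might also infer that case mix cannot be cleanly adjusted for. That is too strong as well. The planned operation is on the schedule used for screening, and patient records are reviewed after consent (11.1.3), so it is known before the envelope is opened and should be recoverable from source. What is missing is a listed field and a prespecified use of it.

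Nor do the documents show that monitoring changes the class of operation. Their only example is a pause to inflate the lung, changes prompted by oximetry are recorded separately, and the surgical-conduct aim appears in the synopsis but not in 6.4. Procedure performed may therefore often match procedure planned; no rate of change is given. It is still the less safe covariate when a pre-randomisation one is available at almost no cost.

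Finally, broad eligibility suits a pilot, and stratified envelopes are partly a matter of preference. Both points are fair. Blocked stacks can also make upcoming assignments easier to predict, since the intervention arm's display is visible to clinicians.

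**Conclusion.** The point holds as a matter of precision and interpretation, not of bias. The scheduled procedure is not captured before randomisation, allocation is not described as stratified on it, and the arm comparison ignores it.

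The size is unknown, because it depends on a procedure mix and an outcome effect that the documents do not give. Over the assumed range the gain from adjustment runs from about 2 percentage points of power (class effect 0.5 SD) to about 7–8 points (1.0 SD). Conditional on an imbalance of at least 10 points, the false-positive rate is about 6% to 9%. For outcomes that hardly depend on the operation the gain would be negligible. The case for acting rests on the low cost and on the pilot's role in choosing endpoints. It is a lower-priority suggestion.

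**What to change.** - **Section 11.1.3.1:** add a field, *scheduled procedure class*, read from the operating-room schedule and recorded before the envelope is opened. Define the classes in advance, for example thoracoscopic/minor versus open/major.
- **Section 15:** prespecify arm comparisons stratified by or adjusted for that class. For continuous outcomes, a van Elteren (stratified rank-sum) test would serve; for binary outcomes, a Mantel-Haenszel analysis or a logistic model with a class term.
- **Section 15:** state that procedure performed and time on single lung ventilation are not covariates in the arm comparison. They can still be reported by arm.
- **Section 11.2.2 (optional):** use separate envelope sets by class. If so, vary the block sizes and conceal them.

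Eligibility need not change. The cost is one extra field and a little more analysis. A case whose plan changes after randomisation stays in its scheduled class, which slightly dilutes the adjustment but keeps the covariate free of any effect of the intervention.

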#### **9.1.2 Exclusion criteria:**

1. Any patient who has participated in a clinical study of an investigational drug or device in the past 30 days
2. Any patient who the principal investigator feels at any time or for any reason should not participate in this clinical study
3. Withdrawal of informed consent for any reason

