### **9.2 Withdrawal Criteria**

All patients have the right to withdraw any point during the trial without prejudice. The investigator can discontinue any subject at any time if medically necessary. If the ability to monitor the cerebral oximetry is data is lost during the conduct of the study for a significant period of time that precludes useful data analysis then the subject will be withdrawn by the principal investigator.

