## **11 PROTOCOL ASSESSMENTS AND PROCEDURES**

The Schedule of Assessments which details the sequence of assessments and procedures is presented in Table 1. Note that as described in Section 7.2 there are four separate periods that this study is divided into that include the following: screening, baseline, intraoperative and immediate postoperative and postoperative follow up.

Table 1: Schedule of Assessments

	Screening	Baseline Acquisition	Intraoperative and Immediate Postoperative	Postoperative Follow Up
Study Assessment				
Review of inclusion/exclusion criteria	X			
Informed consent	X			
Demographics	X			
Medical history	X			
Randomization		X		
MMSE & CAM testing		X		X
Serum creatinine	X			X
Obtain baseline room air and O 2 supplemented rSO 2		X		
Continuous rSO 2 , SpO 2 , blood pressure data collection			X	
Employ rSO 2 desaturation algorithm (intervention group only)			X	
Continuous intra/immediate post-operative clinical variable collection			X	
PACU and ICU clinical variable collection			X	
Postoperative clinical variable collection			X	X
Adverse and Serious Adverse Event Monitoring		X	X	X
Telephone interview				X

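### Exclusion criteria 2 and 3 stay open after randomisation, no rule says all randomised subjects are analysed as assigned, and the target of 100 is counted in two ways

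*Combined protocol and SAP*

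**What the plan says.** **Exclusion rules.** Section 9.1.2 has three exclusion criteria. The second covers "Any patient who the principal investigator feels at any time or for any reason should not participate in this clinical study". The third is "Withdrawal of informed consent for any reason". Neither is tied to a time before allocation.

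**Withdrawal rules.** Section 9.2 separately states that "All patients have the right to withdraw any point during the trial without prejudice". It lets the investigator discontinue a subject on grounds of medical necessity. It also provides that if oximetry data are lost "for a significant period of time that precludes useful data analysis then the subject will be withdrawn by the principal investigator".

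**Timing of eligibility checks.** Section 7.2.1 places the assessment of suitability in the screening period. In Table 1 (section 11) the row "Review of inclusion/exclusion criteria" is marked under Screening only. Section 11.1.3 adds a chart check after consent. Sections 7.2.2 and 11.2.1 then put randomisation ahead of the baseline MMSE, CAM and rSO2 measurements, which are inclusion criteria 2 to 4.

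**Target.** Section 9.1: "A total of 100 evaluable subjects will be enrolled into this protocol". The synopsis: "100 subjects with balanced randomization (1:1) to control (blinded NIRS data) or intervention (open NIRS data) cohorts". Section 7.1 also counts 100 randomised.

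**Analysis.** Section 15 names the tests. It defines no analysis population and does not say how excluded or withdrawn subjects are handled.

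**The concern.** Randomisation makes the arms comparable only if the set of subjects analysed is fixed without regard to arm or outcome. An exclusion criterion should act on facts known before allocation. Criterion 2 has no such limit. It is also wider than 9.2, because it needs neither medical necessity nor lost signal. Criterion 3 puts an event that can happen at any stage of the trial among the eligibility rules.

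The information that could influence such a decision is available. In the intervention arm the clinicians and a research assistant watch the display (section 10.3), while the control display is blank after baseline. Both co-PIs review and sign each adverse event report (section 13.2).

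The primary objective (section 6.2) is to find the outcomes that differ significantly between arms and to design a larger trial around them. Selective removal would distort that choice.

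**Working it through.** **1. The plan's own figure.** The only figure is 100 subjects, 50 per arm. It cannot be re-derived, because no effect size, SD, event rate, power or drop-out is given.

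**2. Can a subject be excluded after allocation?** Set side by side:
- Sections 7.2.1 and 11.1.3 and Table 1 say when eligibility is reviewed. None says that eligibility ends there.
- Criterion 2 expressly applies at any time.
- Inclusion criteria 2 to 4 can be checked only after the envelope is opened, so part of eligibility is necessarily settled after allocation.
- Section 15 has no as-randomised rule that would keep an excluded subject in the analysis.

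So yes: the text permits it.

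**3. How far apart are the two targets?** If *evaluable* means remaining after removals, the number randomised to reach 100 is 100/(1 − d), rounded up, where d is the proportion removed. The plan gives no d, so a range is assumed:
- d = 2%: 100/0.98 → 103
- d = 5%: 100/0.95 → 106
- d = 10%: 100/0.90 → 112
- d = 15%: 100/0.85 → 118
- d = 20%: 100/0.80 → 125

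Under section 7.1 the number is 100 whatever is lost.

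**4. What could selective removal do?** Assume no true effect, 50 per arm, and a two-sided 5% level (sidedness is not stated in the plan). The k worst outcomes are removed from the intervention arm only.

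*Continuous outcome, Wilcoxon rank-sum test:* 20,000 simulated trials, identical lognormal arms. Simulation standard error is at most about √(0.14 × 0.86/20,000) = 0.25 percentage points. Test and removal rule both use ranks only, so any continuous distribution common to both arms gives the same answer apart from simulation error.

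| k removed | Type I error, no replacement | Type I error, with replacement |
|---|---|---|
| 0 | 5.0% | 5.0% |
| 1 | 5.8% | 5.9% |
| 2 | 6.9% | 6.6% |
| 3 | 8.5% | 8.3% |
| 5 | 14.0% | 12.7% |

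Almost all of the excess favours the intervention: 2.6% of trials at k = 0, 7.6% at k = 3 and 13.6% at k = 5, without replacement.

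*Binary outcome, pooled z-test:* exact enumeration, no replacement, assumed common event rates.

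| Event rate | k = 0 | k = 3 | k = 5 |
|---|---|---|---|
| 20% | 5.2% | 12.7% | 26.9% |
| 30% | 5.0% | 9.2% | 16.1% |
| 50% | 5.7% | 6.2% | 9.4% |

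**5. A single balanced data set.** Suppose both arms have 20/50 = 40.0% events (an assumed rate).
- Remove 3 events from one arm: 17/47 = 36.2%. Pooled rate 37/97 = 0.381; z = 0.038/0.099 = 0.39; p ≈ 0.70.
- Remove 4: 16/46 = 34.8%. Pooled rate 36/96 = 0.375; z = 0.052/0.099 = 0.53; p ≈ 0.60.
- Remove 11: 9/39 = 23.1%. Pooled rate 29/89 = 0.326; z = 0.169/0.100 = 1.69; p ≈ 0.09.

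In perfectly balanced data a few removals shift the estimate but do not produce significance. The inflation in step 4 comes from trials in which chance has already put the arms some way apart.

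**The case against.** The strongest reply is that screening is the scheduled point for eligibility review, that catch-all discretion clauses are common, and that this is a hypothesis-generating pilot. On that view criterion 2 would ordinarily be used before allocation, and criterion 3 is misplaced duplication of 9.2. This stands in part: the documents describe no selective use of the clause, and the figures in step 4 are worst cases in one direction, not a forecast. It does not remove the point, because the schedule neither closes eligibility nor limits criterion 2, and a pilot that picks endpoints by significance is exposed to this kind of distortion.

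Three stronger readings are tempting, and the documents do not support them:
- *That excluded subjects are replaced and the loss is hidden.* No replacement rule is stated. Section 9.1 counts subjects enrolled, and section 10.1 has enrolled subjects then randomised, so enrolment precedes allocation. Nothing says removals would go unreported. What stands is that *evaluable* is undefined and the targets disagree.
- *That criterion 3 turns a drop-out into someone who was never eligible and discards the data.* No section says so, and 9.2 treats withdrawal as withdrawal.
- *That three or four exclusions are enough by themselves to create a significant difference.* Step 5 shows p-values of about 0.70 and 0.60.

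**Conclusion.** The point holds as a gap in the rules, not as evidence of what would be done. As written, the plan permits removal after allocation on the investigator's judgement, with arm and course knowable and no as-randomised analysis to contain the effect. The target of 100 also has two meanings that must be reconciled.

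If removals were selective and all in one direction, 3 of 50 would raise the Wilcoxon type I error from 5% to about 8.5%, and 5 of 50 to about 14%. For a binary outcome the corresponding figures depend strongly on the event rate. These rest on no true effect, 50 per arm, two-sided 5%, and removal of the worst outcomes from one arm only. Removals unrelated to outcome would not inflate the error in this way. The change is worth making because it is cheap and bears directly on how the pilot chooses endpoints.

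**What to change.** 1. **Section 9.1.2, criterion 2:** limit it to the time before the randomisation envelope is opened, with the reason recorded on a screening log.
2. **Section 9.1.2, criterion 3:** delete it. Leave consent withdrawal to 9.2, and state there that data collected up to withdrawal are kept.
3. **Sections 7.2.2 and 11.2:** where feasible, complete the checks of inclusion criteria 2 to 4 before the envelope is opened. Both arms have the same open baseline readings, and the control display is blinded only afterwards. Where this is not feasible, report by arm the subjects who fail these criteria after randomisation.
4. **Section 9.1:** state that 100 subjects will be randomised, matching 7.1 and the synopsis.
5. **Section 15:** state that all randomised subjects are analysed as assigned using available data, and that every removal after randomisation, including those under 9.2, is reported by arm and reason.

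The cost is rewording in 9.1, 9.1.2, 9.2 and 15, plus, if item 3 is adopted, opening the envelope later, in the operating room before induction. A few subjects with incomplete data will count toward the 100. The right to withdraw and discontinuation for medical necessity are unchanged.
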